4.1 Inclusion Criteria

Patients eligible for trial must comply with all of the following at the time of randomization:

- Patients must be ≥ 2 years of age and ≤ 21 years of age
- Patients must have a confirmed diagnosis of hematologic malignancy or solid tumor malignancy
- Patients must be undergoing or planned chemotherapy or BMT
- Patients will only be eligible to receive study drug or placebo during a predicted inpatient stay of ≤ 3 days
- Patients must be predicted to have thrombocytopenia $\leq 20,000/\mu\text{L}$ for ≥ 5 days
- Patient must have a platelet transfusion threshold of $\leq 30,000/\mu\text{L}$
- Patients must be >14 days beyond their last dose of PEG-Asparaginase or >72 hours beyond their last dose of Erwinia Asparaginase (with exceptions below)

- Patients must be able to comply with treatment and monitoring

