4.2 Exclusion Criteria

To be eligible for participation in the study, potential subjects must not meet any of the following criteria:

- Diagnosis of acute promyelocytic leukemia
- History of ITP, TTP or HUS
- History of inherited or acquired bleeding disorder
- History of inherited or acquired prothrombotic disorder
- Diagnosis of DIC
- Patient must not have WHO Grade 2 bleeding or greater within 48 hours prior to enrollment or study drug activation
- Patient must not have received PEG-Asparaginase within the 7 day period prior to enrollment. If this product is given within the 8-14 day period prior to enrollment patients are eligible if PT, PTT, INR and fibrinogen are obtained and are within 1.5 times the upper limits of normal.
- Patient must not be receiving tranexamic acid or other anti-fibrinolytic agent or any other agent to promote hemostasis (which includes DDAVP, recombinant Factor VII, Prothrombin Complex Concentrate, Estrogen Derivatives and Progestins)
- Patient must not be receiving therapy with anticoagulation or antiplatelet therapy (which includes heparin infusion, enoxaparin, aspirin. If anticoagulant/antiplatelet therapy is discontinued when platelet count is <50,000/uL patient will be eligible for enrollment)
- Patient must not be receiving platelet growth factors
- Patient has a current/prior history of thromboembolic event within the past six months. If history of thromboembolic event the patient should be >30 days from completion of anticoagulation therapy
- Patient has a current/prior history of sinusoidal obstruction disease
- Patient has visible blood in their urine
- Patient with renal dysfunction (defined in Section 6, Table 2), hemodialysis or with anuria (defined as <10mL urine/hour over 24 hours)
- History of seizures
- Allergy to tranexamic acid
- Pregnancy
- Unwilling to accept blood transfusions
- Requires platelet transfusion threshold higher than study protocol (If the patient is enrolled on study and begins treatment with either the study drug or placebo, and subsequently requires a platelet transfusion threshold greater than the study protocol they will remain on study).

5. Trial Enrollment

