8.1 Day of Enrollment

- Thrombotic Assessment
 - Assessment for thrombotic event will be performed via a review of medical chart notes and relevant imaging studies obtained within the time period from prior assessment. This definition of will apply to all future time points when a thrombotic assessment is completed.
- Demographics and Medical History
 - Weight, Height, BMI
 - Date of Birth
 - Gender
 - Ethnicity
 - Race
 - Primary Diagnosis
 - Including disease, current treatment (Radiation, chemotherapy medications, BMT source, Donor ABO Type and Related/Unrelated Donor)
 - ABO Type
 - Concomitant Medications
- Laboratory Assessment (lab studies obtained within 24H period prior to enrollment do not need to be repeated unless otherwise stated)
 - CBC
 - Serum Creatinine
 - Pregnancy Test (Urine or Serum, if female of child-bearing age and >72 hours from previous)
 - HLA Testing results (if done as part of routine care)
 - Coagulation Testing (PT, PTT, INR and Fibrinogen) if PEG-Asparaginase or Erwinia Asparaginase has been given >7 days but ≤14 days from date of enrollment
- Adverse events related to standard anticancer therapies will be carefully monitored for events that would preclude activation of study drug. Collection and documentation of AEs for the trial will begin following first dose of study drug.

8.2 Days Between Enrollment and Randomization; Days Between Randomization and Activation of Study Drug

- Thrombotic Assessment (via chart review), to be completed once weekly
- Laboratory Assessment, to be completed daily
 - CBC
- Adverse events related to standard anticancer therapies will be carefully monitored for events that would preclude activation of study drug. Collection and documentation of AEs for the trial will begin following first dose of study drug.
- Medication Review – Document new or discontinued medications

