8.3 Day of Randomization

- Hemostatic/Bleeding Assessment
 - Bleeding will be recorded using the WHO Bleeding score as the bleeding assessment tool. Bleeding assessments will be completed by means of a physical assessment of the patient, patient interview and a review of patient chart and laboratory data for documented bleeding events. Research staff which will be either research nurse, primary investigator or co-investigator, will perform physical assessment of the patient and interview prior to reviewing the patient's medical chart and laboratory data to allow an objective assessment. Nursing staff may provide additional details. If participant has had WHO Grade 2 or higher bleeding within 48H of randomization they will not be randomized. They will be eligible for randomization if bleeding later resolves. This definition of hemostatic/bleeding assessment will apply to all further time points at which a bleeding assessment is completed.
 - If participant has had WHO Grade 2 or higher bleeding within 48H of randomization they will not be randomized. They will be eligible for randomization if bleeding later resolves.
- Thrombotic Assessment (via chart review)
- Laboratory Assessment (lab studies obtained within 24H period prior to randomization do not need to be repeated unless otherwise stated)
 - Coagulation Profile (PT, PTT, INR, Fibrinogen, D-Dimer)
 - CBC
 - Serum Creatinine
 - Pregnancy Test (Urine or Serum, if female of child-bearing age and >72 hours from previous)
 - Urinalysis (if >72 hours from previous)
- Data on Platelet Transfusions
 - Number of platelet units transfused
 - Source of platelet transfusions (apheresis or whole blood)
 - HLA or cross-match compatible
 - Reason for Transfusion
- Data on Red Blood Cell Transfusions
 - Number of units transfused
 - Reason for transfusion
- Adverse events related to standard anticancer therapies will be carefully monitored for events that would preclude activation of study drug. Collection and documentation of AEs for the trial will begin following first dose of study drug
- Medication Review – Document new or discontinued medications

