 2. To be collected at one time point on day 5 (+/- 1 day), at least six hours after administration of the last study drug dose and before the next dose due
 3. Urinalysis does not need to be repeated if within 72 hours of previous.
 4. If patient has received PEG-Asparaginase or Erwinia Asparaginase >7 and ≤14 days from day of enrollment collect PT, PTT, INR and Fibrinogen **only**
 5. Urine pregnancy does not need to be repeated if within 72 hours of previous.
 6. Once weekly while on study drug
 7. To be completed once weekly by chart review
- * If obtained as part of routine care

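### In the 8-14 day PEG-asparaginase window, the fibrinogen part of the coagulation condition has only an upper bound, so it cannot exclude a patient for a low result

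*Combined protocol and SAP*

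**What the plan says.** The general rule is in section 4.1: "Patients must be >14 days beyond their last dose of PEG-Asparaginase", subject to exceptions. Section 4.2 bars enrollment within 7 days of PEG-asparaginase and then supplies the exception. It opens with "If this product is given within the 8-14 day period prior to enrollment" and continues "patients are eligible if PT, PTT, INR and fibrinogen are obtained and are within 1.5 times the upper limits of normal".

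Three other places deal with the same tests:

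- Section 8.1, day of enrollment: "Coagulation Testing (PT, PTT, INR and Fibrinogen) if PEG-Asparaginase or Erwinia Asparaginase has been given >7 days but ≤14 days from date of enrollment".
- Section 8.3, day of randomization, for all patients: "Coagulation Profile (PT, PTT, INR, Fibrinogen, D-Dimer".
- Footnote 4 to Table 3 (schedule of events), for both asparaginase products over the same interval: "collect PT, PTT, INR and Fibrinogen", and nothing beyond those tests.

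These say what is drawn and when. None says what result is acceptable.

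**The concern.** The coagulation condition is the only stated ground for relaxing the 14-day washout after PEG-asparaginase. Fibrinogen is listed as a test in its own right, so a reader expects its result to be able to change the eligibility decision. A ceiling defined from the upper limit of normal suits tests where the abnormal result of interest is a prolonged one. Applied unchanged to fibrinogen, it leaves the low side open.

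At stake is how much protection the screen gives. The Background section says that current bleeding and coagulation disorders will be excluded as extra caution. Staff completing the eligibility checklist have only the section 4.2 wording to apply. On that item, a very low fibrinogen has to be marked as meeting the condition.

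**Working it through.** The plan gives no figure to reproduce, and no sample size, power or error rate depends on this rule. The check is one of logic, followed by a search for a lower limit elsewhere.

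**Step 1. The rule as a condition.** Write ULN and LLN for the upper and lower limits of normal of each test. Read literally, a patient in the 8-14 day window is eligible on this item if all four hold:

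- PT ≤ 1.5 × ULN
- PTT ≤ 1.5 × ULN
- INR ≤ 1.5 × ULN
- fibrinogen ≤ 1.5 × ULN

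**Step 2. The fibrinogen component alone.** A low result means fibrinogen < LLN. Since LLN < ULN < 1.5 × ULN, every value from 0 up to LLN meets the fourth condition. The only results that fail it are those above 1.5 × ULN. No result is both low and failing.

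**Step 3. The other three components.** For PT, PTT and INR a prolonged result lies above ULN, and the bound rejects those above 1.5 × ULN. There the rule works as a screen.

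**Step 4. The four together.** The conditions are joined by *and*. A patient with low fibrinogen is rejected on this item if PT, PTT or INR exceeds its limit, and is accepted if all three are within it. The gap is therefore low fibrinogen with PT, PTT and INR each at or below 1.5 × ULN.

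**Step 5. Is there a lower limit anywhere else?**

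| Place | What it gives on fibrinogen or coagulation | Lower limit? |
|---|---|---|
| Section 1 summary criteria | 14-day inclusion and 7-day exclusion; omits the 8-14 day condition | No |
| Section 2 Background | Intent to exclude coagulation disorders; no laboratory definition | No |
| Section 4.2, other items | DIC; "History of inherited or acquired bleeding disorder"; both rest on diagnosis | No |
| Section 8.1 | Collection at enrollment | No |
| Section 8.3 | Collection at randomization | No |
| Table 3, footnote 4 | Collection only | No |
| Table 4 | Sample volume | No |

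**Step 6. Erwinia asparaginase.** Section 8.1 and Table 3 footnote 4 require the tests after either product when it was given more than 7 and at most 14 days before enrollment. The acceptance rule in section 4.2 refers to PEG-asparaginase alone. For Erwinia, section 4.1 asks only for more than 72 hours since the last dose, so a patient 8 to 14 days out already meets the washout. The tests are drawn, but no stated criterion applies to the results.

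**The case against.** Several points on the other side have force.

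- **The screen is wider than fibrinogen.** A reader might infer that any patient with low fibrinogen passes the whole coagulation screen. The documents do not support that: PT, PTT and INR must also be within their limits (Step 4). This stands, and the point is confined to the fibrinogen component.
- **An upper cap may be deliberate.** A reader might infer that a floor was intended and the drafters made a slip. The documents do not say so. The Background names thromboembolism as a major concern with this class of drug, and section 4.2 excludes prothrombotic disorders, so a ceiling is conceivable. They do not say a ceiling was intended either. What stands is that the direction is unstated.
- **Other safeguards exist.** Section 4.2 excludes DIC, bleeding disorders and recent WHO grade 2 or greater bleeding. The randomization-day profile in section 8.3 would bring a low value to notice before study drug starts. Section 6.3 stops study drug if an exclusion emerges or was missed, and allows withdrawal for any reason. These reduce the safety consequence. None carries a fibrinogen value, so they leave the wording gap open.
- **Bleeding comparisons are not biased by it.** A reader might infer that the rule damages comparability of bleeding outcomes between arms. Eligibility is applied before blinded 1:1 randomization in blocks of four, so the same criterion governs both arms and creates no systematic difference. Bleeding is also a secondary endpoint for which section 11.7 disclaims power.
- **Exposure is narrow.** The window is counted back from enrollment, while activation waits for platelets of 30,000/µL or less (section 5.2), so some of these patients may receive their first dose after day 14. Patients outside the window face no fibrinogen floor either. Both points limit the size of the problem. Neither explains why a test required for the exception can act in one direction only.

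**Conclusion.** The point holds for the fibrinogen component. As written in section 4.2, no low fibrinogen result can fail it, and no other section supplies a lower limit. A patient in the 8-14 day PEG-asparaginase window with a low value is stopped only by PT, PTT or INR above the limit, or by a diagnosis-based exclusion.

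The size in patients cannot be given, because the documents do not say how many of the 20 planned activated subjects would fall in this window. For scale only, one such patient would be 1/20 = 5% of the activated sample. The consequence is limited to eligibility and safety screening in that window.

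The conclusion rests on the literal reading of the bound as an upper limit for each of the four tests. It does not depend on which side the clinical team had in mind: if a ceiling was meant, saying so would settle the matter. The missing acceptance rule after Erwinia asparaginase is a separate gap in the same provision.

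**What to change.** In section 4.2, take fibrinogen out of the shared bound and give it its own condition, stating the direction and the limit. Both are for the clinical team to set; none is proposed here. PT, PTT and INR can keep their present wording.

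In the same edit, reconcile section 4.2 with section 8.1 and Table 3 footnote 4. State whether the results drawn after Erwinia asparaginase bear on eligibility, and if so by what rule, or else say that they are collected for information only. The Section 1 summary should also show the 8-14 day condition, which it now omits.

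The cost is small. The change is a line of eligibility wording and matching checklist text, with no new test, visit or sample, and no effect on the sample size. The downside is that, depending on the limit chosen, some early-window patients may have to wait until more than 14 days after the dose. Their number is not given.

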5.1 Screening and Recruitment

Potentially eligible subjects will be identified by the investigator or trained member of the research staff. All new admissions to the Oncology or Bone Marrow Transplantation

service will be screened on a daily basis for potential eligibility based on underlying diagnosis and an expected period of thrombocytopenia $\leq 20,000/\mu\text{L}$ lasting ≥ 5 days. Patients who will be undergoing BMT may also be identified by their primary transplant physician at the time of their consent for BMT. Following initial identification of eligibility, the primary investigator or member of the research staff will screen subjects for full enrollment eligibility using medical history and laboratory results. There will not be a screening consent, we will seek a waiver of consent for screening purposes only. Screening eligibility checklist will be maintained in trial file in order to track information on screening and consent metrics at trial end. There will be no identifiable protected health information recorded on screening forms for patients who do not meet eligibility requirements or who decline trial enrollment. Patients who are screened for eligibility and meet requirements will be assigned a case ID which will be used to identify the participant on all subsequent trial documentation. The names of all patients screened for eligibility will be recorded on a separate screening log sheet in order to avoid double-screening.

After obtaining permission from the subject's physician to discuss the study, the primary investigator or trained research staff member will contact the prospective subject and obtain study consent. After signing the study consent the subject will be enrolled on to the study.

5.2 Randomization

This trial is designed as a prospective, randomized, controlled, blinded (patient, caregiver, physician, assessor) trial with two parallel groups and a primary endpoint of feasibility and safety. Randomization will be performed as block randomization with a 1:1 allocation within blocks of size four.

When a consented participant's platelet count falls to $\leq 50,000/\mu\text{L}$ and the platelet count is expected to continue to fall and remain $\leq 20,000/\mu\text{L}$ for 5 days or longer, the patient will be randomized to either the tranexamic acid arm or the placebo arm by the investigational pharmacy. When the randomized subject's platelet count is $\leq 30,000/\mu\text{L}$ with an expectation that the platelet count will be $\leq 20,000/\mu\text{L}$ for 5 days or longer the study drug will be activated. Activation of the study drug will act as time point zero for all study endpoints.

5.3 Enrollment Period

Screening will continue until the target population is achieved (20 activated subjects total). The enrollment period will extend over 18 months. The expected enrollment is estimated to be 14 randomized subjects per year. Both arms will have a target enrollment of 10 activated subjects

6. Interventions

6.1 Study Drug (Tranexamic Acid or Placebo)

Tranexamic acid forms a reversible complex that displaces plasminogen from fibrin resulting in inhibition of fibrinolysis. Patients who are randomized to receive tranexamic acid will receive 10mg/kg IV Q8h by default, TID dosing will also be acceptable if it allows for fewer breaks into the line to reduce the risk of central-line associated

infections. Patients will continue tranexamic acid until they meet criteria for stopping the study drug as provided in section 6.3. Criteria for temporary discontinuation of the study drug are given in section 6.4.

Tranexamic acid is a clear, colorless liquid in IV form. Patients randomized to the control arm will receive matching placebo, which will be IV normal saline of a volume equivalent to what the patient's dose of tranexamic acid would be.

Rationale for dose:

According to the Children's Hospital of Pittsburgh formulary through Lexicomp, the dosing of tranexamic acid for use in prevention of bleeding associated with tooth extraction in hemophilia patients is 10mg/kg three to four times daily by IV. For the prevention of bleeding associated with surgical procedures (cardiac and spinal procedures) continuous IV infusions of tranexamic acid have been used. In pediatric cardiac surgery, TXA dosing ranges from 100mg/kg IV bolus followed by a continuous infusion of 10mg/kg/hour IV infusion to a loading dose of 6.4mg/kg followed by a continuous infusion in the range of 2 to 3.1mg/kg/hour. In pediatric non-cardiac surgery the range of doses used in pediatric randomized trials is shown below. They range from 100mg/kg IV load following by a continuous infusion of 10mg/kg/hour to 10mg/kg IV load to 1 mg/kg/hour infusion in in pediatric patients undergoing spinal surgery [12, 23-26]. Long-term prophylaxis in children with hereditary angioedema uses doses of 20 to 75mg/kg/day in two to three divided doses, administered orally. In cases of traumatic hyphema, tranexamic acid is dosed orally at 25mg/kg/dose every eight hours for five to seven days.

The dose chosen for this study is in the low -range of recommended IV doses for pediatric indications.

Table 1: Tranexamic acid dosing in pediatric non-cardiac surgery trials

Author	Design	Number	Age	Dose	Effect
Neilipovitz 2001	TXA vs placebo (RCT)	44	8-18	10mg/kg 1mg/kg/hr	Significant reduction in blood loss -250mls (-1123 to 623mls)
Sethna 2005	TXA vs placebo (RCT)	40	9-18	100mg/kg 10mg/kg/hr	Significant reduction in blood loss -855mls (-1408 to -301mls) NS reduction in blood transfusion 0.85 (0.56-1.30)
Ng 2016	TXA vs placebo (retrospective cohort)	90 (55/35)	10-23	100mg/kg 10mg/kg/hr	Blood loss decreased by 1.8L vs 3.9L p<0.01, blood transfusion decreased by 77%
Goobie 2011	TXA vs placebo (RCT)	43	2 months – 6 years	50mg/kg 5mg/kg/hr	Significant reduction in blood loss 65mls/kg vs 119mls/kg and blood transfusion 33 vs 56mls/kg
Dadure 2011	TXA vs placebo (RCT)	40	3-15 years	15mg/kg 10mg/kg/hr	Significant reduction in blood loss 7.2mls/kg vs 16.6mls/kg NS reduction in blood transfusion 37% vs 70%

6.2 Concomitant Care

Patients enrolled on trial must have a prophylactic platelet transfusion threshold of $\leq 10,000/\mu\text{L}$ (for patients with solid tumors or hematologic malignancies not undergoing BMT) or $\leq 20,000/\mu\text{L}$ (for patients undergoing BMT) at the time of randomization. Prophylactic platelet transfusions will be given when morning platelet count is below the above values for prophylactic transfusions. Therapeutic platelet transfusions above these thresholds will be allowed at the discretion of their treating physician (for cases including active bleeding, for an expected platelet count of $\leq 10,000$ or $\leq 20,000/\mu\text{L}$ the following morning, planned invasive procedures with the need for an increased platelet threshold or trauma). Clinicians will be allowed to exercise discretion to transfuse platelets for any reason should they feel there is a clinical reason to do so. In cases where a platelet transfusion is given for invasive procedures or trauma the subject will return to the study platelet transfusion threshold following this event when determined safe to do so by the treating physician. If, following enrollment and study drug activation, the subject subsequently has an event which leads to the need for a platelet transfusion threshold of greater than the study protocol, they will remain on study.

Type and dose of platelet transfusion will not be specified. If a patient appears to develop platelet refractoriness (which is defined as two sequential transfusions with a repeat platelet count after a 4hour period of $\leq 5000/\mu\text{L}$) then clinicians may exercise their judgement as to use of matched platelets or alloantibody testing. Data on type of platelet transfusion administered will be collected. For any platelet transfusions given

above the study threshold the rationale will be recorded on the daily transfusion assessment form.

Patients will receive red blood cell transfusions as per the standard care of their treating physician.

No other medication changes are directed in this protocol and standard care will otherwise be followed.

